1 SYNOPSIS

CLINICAL INVESTIGATION TITLE: A Prospective, Randomized, Controlled Study Assessing Vagus Nerve Stimulation in CoViD-19 Respiratory Symptoms (SAVIOR II)

CLINICAL INVESTIGATION CODE:

2020-132-AGH

CLINICAL INVESTIGATIONAL MEDICAL DEVICE(S):

gammaCore Sapphire® (non-invasive vagus nerve stimulator)

OBJECTIVES:

The aims of this study are to summarize and compare the incidence of clinical events and pro-inflammatory cytokine levels in patients randomized to use of gammaCore Sapphire plus standard of care vs standard of care alone in patients hospitalized for CoViD-19. In addition, this study is intended to demonstrate the safety of gammaCore Sapphire use in patients hospitalized for CoViD-19.

Specific clinical events to be summarized include, but are not limited to:

- Changes in oxygen support requirements (no oxygen support, low-flow oxygen support, nasal high-flow oxygen support, noninvasive mechanical ventilation, and invasive mechanical ventilation)
- Changes in O₂ saturation
- PaO₂/FiO₂ ratio
- Proportion of subjects requiring mechanical ventilation
- Days to onset of mechanical ventilation
- Live discharge from the hospital
- Patient length of stay
- Mortality
- Shortness of Breath
- Clinical improvement Scale

Specific laboratory measurements to be summarized include, but are not limited to:

- TNF- α
- IL-1 β
- IL-6
- CRP
- Ferritin
- D Dimer

- Pro-Calcitonin

OVERALL CLINICAL INVESTIGATION DESIGN:

The study is a prospective, randomized, controlled investigation designed for comparison of two groups for the reduction of respiratory distress in a CoViD-19 population, using gammaCore Sapphire® (nVNS) plus standard of care (active) vs. standard of care alone (SoC), the control group. The gammaCore® (nVNS) treatments will be used acutely and prophylactically.

Prophylactic

Administer one treatment of gammaCore®, scheduled three times a day (morning, mid-day and 1 hour before bed at night)

One treatment is defined as 2 consecutive doses (stimulations). Each dose delivers a 2-minute stimulation. One dose is applied to the left side of the neck, then one is applied to the right side

SoC: No Administration of gammaCore®

AND

Acute respiratory failure (w/hypoxia) or Shortness of breath

Administer one treatment of gammaCore® for acute treatment of shortness of breath (as needed, up to nine times a day)

One treatment is defined as 2 consecutive doses (stimulations). Each dose delivers a 2-minute stimulation. One dose is applied to the left side of the neck, then one to the right. If shortness of breath (SOB) persists 20 minutes after start of first treatment, administer a second treatment. If the additional treatments do not appear to be providing benefit/relief of symptoms (as per patient or physician discretion) there is no need to continue with additional acute treatments. However, if it there appears to be benefit, the patient can administer more as needed. The patients can receive up to 9 acute treatments (or 18 stimulations) per day.

SoC: No Administration of gammaCore®

INCLUSION AND EXCLUSION CRITERIA:

Inclusion Criteria

All patients must meet the following inclusion criteria to be included in this study:

1. Patients (age 18 years and older) who have tested positive or suspected/presumed positive for CoViD-19 (PCR real time test)
2. Patients with cough, shortness of breath or respiratory compromise (RR>24/min, increased work of breathing.)
3. O₂ Saturation less than or equal to 96% on room air or sensation
4. Agrees to use the gammaCore Sapphire device as per protocol and to follow all of the requirements of the study including recording required study data
5. Permission for early am blood draw to freeze for subsequent lab tests and sequencing as related to CoViD-19 sequelae
6. Patient is able to provide signed and witnessed Informed Consent

Exclusion Criteria

Patients meeting any of the following criteria cannot be included in this research study:

1. On home/therapy oxygen (i.e. for COPD patients) at baseline prior to development of CoViD-19
2. Already using gammaCore® (nVNS) for other medical conditions
3. A history of aneurysm, intracranial hemorrhage, brain tumors, or significant head trauma
4. Known or suspected severe atherosclerotic cardiovascular disease, severe carotid artery disease (e.g., bruits or history of transient ischemic attack or cerebrovascular accident), congestive heart failure, known severe coronary artery disease, myocardial infarction documented within past 90 days, or current or recent history of life-threatening arrhythmia (sustained ventricular tachycardia, ventricular fibrillation, second or third-degree heart block, uncontrolled atrial fibrillation or

uncontrolled atrial flutter)

5. Patients with clinically significant hypertension, hypotension, bradycardia, or tachycardia (as per investigator discretion)
6. Current implantation of an electrical and/or neurostimulator device, including but not limited to a cardiac pacemaker or defibrillator, vagal neurostimulator, deep brain stimulator, spinal stimulator, bone growth stimulator, or cochlear implant
7. Current implantation of metal cervical spine hardware or a metallic implant near the gammaCore® stimulation site
8. Belongs to a vulnerable population or has any condition such that his or her ability to provide informed consent, comply with the follow-up requirements, or provide self-assessments is compromised (e.g. homeless, developmentally disabled and prisoner)
9. Compromised access to peripheral veins for blood sampling.
10. Pregnant women
11. Patients with active cancer or those who have had recent cancer treatment

CLINICAL INVESTIGATION PROCEDURE OVERVIEW:

Enrollment / Admission Day - Day 0

Study patient must meet all of the following inclusion criteria and none of the exclusion criteria

- Patient must sign Informed Consent and witness to signature must occur
- Randomization – Upon meeting all eligibility requirements (including verification of +CoViD-19 testing), patient's will be randomized 1:1 into either the control group or the treatment group
- Intake Collection of:
 - Basic Demographics
 - Date of Birth (DOB), Race, Sex, Smoking Status, County/Region
 - Medications, Co-morbidities

- CoViD-19 Test Results (Positive / Presumed Positive)
- Study Measurements:
 - Height/Wt (BMI)
 - Temperature
 - Blood Pressure
 - O₂ Saturation
 - PaO₂/FiO₂ ratio
 - Shortness of Breath (Yes / No)
 - Cough (Yes / No)
- Clinical Labs
 - Immunokine panel (TNF-α, IL-1β, IL-6)
 - Frozen blood sample
 - Leukocyte flow cytometry
 - Pro-Calcitonin
 - CRP
 - Ferritin
 - D Dimer
 - Complete hematology panel (CBC with differential)
 - Comprehensive metabolic panel
 - Serum or urine hCG (for any woman who might be pregnant)
- Device training: Patient receives device training on gammaCore® Sapphire device and receives first treatment with trained study staff*
 - VNS Stimulation Supervised**, record date and times of stimulations
 - Daily Tx Log Completion
 - Oxygen Required, Oxygen level (%) based on device type (HFNC / NC / Bipap / Optiflow), Ventilator Dependence, Date and time of Ventilation, Patient discharge home, Date and time of Discharge, Survival
- Clinical Improvement Ordinal Scale
 - Adverse event assessment

* For those patients allocated to non-invasive vagus nerve stimulation, the patient will be instructed by a study physician or study personnel on the gammaCore® technique. They will be instructed to use it according to the specified protocol, which will be available at bedside.

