7.2.1 Schedule of Clinical Investigation Events

7.2.1.1 Intake / Admission (Day 0)

Upon hospital admission, after the patient and the Investigator have signed the Informed Consent Form, the patient will be randomized 1:1 into one of the two treatment arms. Patient's severity of condition will be classified based on age, co-morbidities, and oxygen saturation as moderate or severe. To prevent allocation bias, the patient will be assigned to the test or control arm of the study based on severity of classification in a 1:1 ratio. Thereafter, the study physicians and/or attending physicians participating in the study and if feasible, will conduct a complete physical examination and obtain vitals. Medical and demographic information in the EMR pertinent to this trial and the patient's treatment will also be captured into the CRFs.

The following Intake and collection of data will then be conducted:

- Intake Collection of:
 - Basic Demographics
 - Date of Birth (DOB), Race, Sex, Smoking Status, County/Region
 - Medications, Co-morbidities
 - CoViD-19 Test Results (Positive / Presumed Positive)
- Study Measurements:
 - Height/Wt (BMI)
 - Temperature
 - Blood Pressure
 - O₂ Saturation
 - PaO₂/FiO₂ ratio
 - Shortness of Breath (Yes / No)
 - Cough (Yes / No)
- Clinical Labs
 - Immunokine panel (TNF- α , IL-1 β , IL-6)
 - Frozen blood sample[†]
 - Leukocyte flow cytometry
 - Pro-Calcitonin

- CRP
- Ferritin
- D Dimer
- Complete hematology panel (CBC with differential)
- Comprehensive metabolic panel
- Serum or urine hCG (for any woman who might be pregnant)
- Device training: Patient receives device training on gammaCore® Sapphire device and receives first treatment with trained study staff *
 - nVNS Stimulation Supervised**
 - Study log completion: patient will record date and times of stimulations.
 - Daily Tx Log Completion
 - Oxygen Required, Oxygen level (%) based on device type (HFNC / NC / Bipap / Optiflow), Ventilator Dependence, Date and time of Ventilation, Patient discharge home, Date and time of Discharge, Survival
 - Clinical Improvement Scale
 - Adverse event assessment

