7.4.2 Inclusion Criteria

The patients have to meet all of the following criteria to be eligible to enter the investigation:

1. Patients (age 18 years and older) who have tested positive or suspected/presumed positive for CoViD-19 using PCR real-time test
2. Patients with cough, shortness of breath or respiratory compromise (RR>24/min, increased work of breathing)
3. O₂ Saturation less than or equal to 96% on room air or sensation
4. Agrees to use the gammaCore Sapphire device as per protocol and to follow all of the requirements of the study including recording required study data
5. Permission for early am blood draw to freeze for subsequent lab tests and sequencing as related to CoViD-19 sequelae
6. Patient is able to provide signed and witnessed Informed Consent

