7.4.4 Removal of Patients from the Clinical Investigation

Patients are free to discontinue participation in the investigation at any time, without prejudice to further treatment. Patients who discontinue the investigation should always be asked about the reason(s) for their discontinuation and about the presence of any adverse event (AE)/adverse device effect (ADE) and, if possible, be assessed by a Clinical Investigator.

Patients may be withdrawn from investigation treatment and assessments at any time, if deemed necessary by the Clinical Investigator.

Specific reasons for withdrawal of patients from this investigation are:

- The decision of a patient to withdraw from the investigation (including if the patient withdraws informed consent)
- Unacceptable adverse event
- Patient lost to follow-up; or
- Patient is non-compliant with study procedure

In case of withdrawal, AEs/ADEs should be followed up.

Incorrectly enrolled patients will be withdrawn from further investigation and assessments. A protocol deviation will be submitted to the IRB via a prompt report form.

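### Presumed-positive patients meet inclusion criterion 1 but fail the synopsis condition for randomisation, and the rule for incorrectly enrolled patients could then cost outcome data

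*Combined protocol and SAP*

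**What the plan says.** **Eligibility.** Inclusion criterion 1 in the synopsis covers patients "who have tested positive or suspected/presumed positive for CoViD-19 (PCR real time test"). Section 7.4.2 has the same rule: "who have tested positive or suspected/presumed positive for CoViD-19 using PCR real-time test".

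**Randomisation.** The synopsis, under Day 0, randomises 1:1 once every eligibility requirement is met, "including verification of +CoViD-19 testing". Section 7.2.1.1 randomises once the consent form is signed and mentions no check of a test result.

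**Recording.** The intake list, both in the synopsis and in section 7.2.1.1, has the field "CoViD-19 Test Results (Positive / Presumed Positive"). Footnote a to Table 1 places test results under intake, and intake is marked at admission only.

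**Withdrawal.** Section 7.4.4 says: "Incorrectly enrolled patients will be withdrawn from further investigation and assessments". It adds that a protocol deviation goes to the IRB and that adverse events and device effects are followed up after withdrawal. It does not define who counts as incorrectly enrolled.

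**The concern.** A patient without a positive result satisfies inclusion criterion 1 and fits the intake field, yet fails the randomisation condition in the synopsis. Two staff members who each follow the protocol could decide differently about that patient.

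The second issue is what follows if the patient is randomised. Someone applying the synopsis condition afterwards could call the enrolment incorrect, and section 7.4.4 would then end the outcome assessments. The control arm receives no device, so site staff know the allocation when that judgement is made. Oxygen support, ventilation, discharge, mortality and serial cytokines are all collected through daily study assessments, so stopping those assessments removes the data the comparison depends on.

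**Working it through.** The plan contains no figure on this point to reproduce. The check is mainly a comparison of passages.

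**Step 1: the test-status rule, place by place**

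| Place | Presumed positive accepted? |
|---|---|
| Synopsis, inclusion criterion 1 | Yes |
| Section 7.4.2, inclusion criterion 1 | Yes |
| Synopsis, Day 0 randomisation step | No, on its plain wording |
| Synopsis, Day 0 intake field | Yes |
| Section 7.2.1.1, randomisation | No verification step |
| Section 7.2.1.1, intake field | Yes |

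One place out of six requires a verified positive. The reference to PCR in both versions of criterion 1 does not settle the matter. A patient who is only suspected has no positive PCR result, so the phrase cannot govern both limbs without emptying the second.

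**Step 2: what happens to a randomised presumed positive**

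- Section 7.4.3 ends by setting the standard for enrolment: all inclusion criteria met and no exclusion criterion. On that standard the patient is correctly enrolled.
- On the synopsis condition the patient should not have been randomised, and could be called incorrectly enrolled.
- In the second case section 7.4.4 stops assessments. Section 7.12 promises continued follow-up only when discontinuation is for safety or lack of effectiveness, so it does not restore them.

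**Step 3: what happens in the analysis**

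- Section 7.10.1.1 analyses the ITT population by randomised arm and has no exclusion for test status. Its condition of at least one verified treatment is a separate matter.
- Section 7.10.2 keeps available data from withdrawn patients as far as possible.
- The patient is therefore not dropped from analysis. What is lost is the data that would have been collected after withdrawal.

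**Step 4: scale**

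Section 7.4.1 gives up to 60 patients, 30 per arm (2 × 30 = 60). One patient is 1/30 = 3.3% of an arm.

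The share of presumed positives is not given. As an assumption only, take 5% to 30% of 60:

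- 0.05 × 60 = 3 patients and 0.30 × 60 = 18 patients under conflicting rules.
- If all of them lost their outcome data, evenly by arm, the number per arm would average (60 − 3)/2 = 28.5 to (60 − 18)/2 = 21.
- 95% CI half-width for a difference in proportions, both near 50%: 1.96 × √(2 × 0.25/n).
- n = 30: 0.253. n = 28.5: 0.260. n = 21: 0.302.

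This is a worst case for precision within the assumed range, because it treats every presumed positive as withdrawn with no usable outcome. It says nothing about bias.

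**The case against.** The best reply is that this is a single stray phrase. Verification appears only in the synopsis, every other place accepts presumed positives or is silent, and the enrolment standard in section 7.4.3 treats such patients as eligible. Taken strictly, the synopsis condition applies before randomisation, so the patient would never enter. Withdrawal afterwards needs one person to overlook the condition and another to apply it later. Section 7.4.4 also requires each incorrect enrolment to be reported to the IRB, which limits quiet discretion. Section 7.10.4 reports only minor deviations in the first 20 patients, with nothing reportable. Finally, sections 7.10.1.2 and 7.10.3 call all comparisons nominal.

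Most of this stands and limits the size of the point. It does not remove the conflict, because no passage says which rule prevails. A looser reading of the synopsis phrase, as confirming whatever status criterion 1 allows, is possible but is not its plain meaning. Section 7.10.4 does not say how many of the 20 were presumed positive or how they were classified.

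A reader might infer three stronger conclusions, and the documents support none of them:

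- **These patients are excluded after randomisation.** Section 7.4.4 ends assessments. It does not remove anyone from an analysis set.
- **Staff would remove patients according to arm.** Allocation is visible, so the opportunity exists, but test status is recorded at Day 0 and nothing shows it being used in this way.
- **The treatment effect is diluted by a stated percentage.** The documents give no share of presumed or uninfected patients. Section 5.1 also proposes an effect on bronchoconstriction that need not depend on infection. Any dilution would come from the choice to admit presumed positives, not from the contradiction.

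**Conclusion.** The contradiction is real and should be corrected. Its consequence is a risk: outcome data could be lost after randomisation for patients whose eligibility depends on which passage is read. That risk depends on two things the documents do not establish, namely that some presumed positives are randomised and that some of them are later judged incorrectly enrolled.

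The only size that follows from the plan is 3.3% of an arm per patient. The widening of the interval from 0.253 to between 0.260 and 0.302 holds only under the assumed 5% to 30% share and complete loss of those patients' outcomes. The case for acting is that allocation is known, the arms are small and the remedy is cheap. No harm to date is shown.

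**What to change.** 1. **One test-status rule.** Reconcile inclusion criterion 1 (synopsis and section 7.4.2), the synopsis Day 0 randomisation step, section 7.2.1.1 and both intake fields. Which rule to keep is for the sponsor and investigator to decide.
2. **Section 7.4.4.** Define who is incorrectly enrolled. Delete the reference to assessments, so that an incorrectly enrolled patient who has been randomised continues outcome follow-up, subject to consent. Whether such a patient goes on using the device is a clinical matter on which this point takes no position.
3. **Section 7.10.1.1 and the SAP.** State that these patients stay in the main analysis in their randomised arm.
4. **If presumed positives are kept,** add a sensitivity table restricted to PCR-confirmed patients.

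The cost is amendment wording, one additional table if item 4 applies, and continued assessment of any patient concerned. Intake records Day 0 status only, so the table also needs the final PCR result taken from the medical record. Without it, patients confirmed after Day 0 would be misclassified.

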**** Protocol:**

Prophylaxis: Administer gammaCore® Sapphire daily, prophylactically, scheduled three times a day (morning, mid-day and 1 hour before bed at night). One treatment is defined as 2 consecutive doses (stimulations). Each dose delivers a 2-minute stimulation. One stimulation is applied to the left side of the neck, then one is applied to the right. This would be a total of 6 treatments (2 stimulations x 3 times per day).

For acute respiratory distress or shortness of breath (SOB): Administer one treatment of gammaCore® for acute treatment of shortness of breath (as needed, up to nine times a day). One treatment is defined as 2 consecutive doses (stimulations). Each dose delivers a 2-minute stimulation. One stimulation is applied to the left side of the neck, then one to the right. If shortness of breath (SOB) persists 20 minutes after start of first treatment, administer a second treatment. If the additional treatments do not appear to be providing benefit/relief of symptoms (as per patient or physician discretion) there is no need to continue with additional acute treatments. However, if it there appears to be benefit, the patient can administer more as needed. The patients can receive up to 9 acute treatments (or 18 stimulations) per day.

Day 1 - 3

For days 1 through 3, the following assessments will be recorded each day:

- Study Measurements:
 - Height/Wt, BMI, Temperature, Blood Pressure, O₂ Saturation, PaO₂/FiO₂ ratio, Shortness of Breath, Cough
- Labs (Research) Early am blood draw (before 10 am) *****Day 1 and 3 only** (then drawn on all odd days)***
 - Immunokine panel (TNF- α , IL-1 β , IL-6), Frozen blood sample, Leukocyte flow cytometry
- Labs (Standard of care) *****Day 1 and 3 only** (then drawn on all odd days)***
 - Pro-Calcitonin, C-reactive protein, Ferritin, D Dimer, CBC with differential
- Comprehensive metabolic panel *****Day 3 only** (then drawn on all odd days)***
- VNS Stimulation supervised
 - Total number of gammaCore® treatments administered, Date and times of stimulations
- Daily Tx Log
 - Oxygen Required, Oxygen level (%), Ventilator Dependence, Date and time of Ventilation, Patient discharge home, Date and time (in 24 hour

format) of Discharge, Survival

- Clinical Improvement Ordinal Scale
- Concomitant medication and adverse event assessments

All Even Days Starting Day 4

- Study Measurements
 - Temperature, Blood Pressure, O₂ Saturation, Shortness of Breath, Cough
- VNS stimulations
 - Total number of gammaCore® treatments administered with Date/time
- Daily Tx Log
 - Oxygen Requirements, Oxygen level (%), Ventilator Dependence, Date and time of Ventilation, Patient discharge home, (if applicable) Date and time of Discharge, Survival
- Clinical Improvement Ordinal Scale
- Concomitant medication and adverse event assessments

All Odd Days Starting Day 5

Same as Days 1 and 3

Study Completion

The last day of the study will be determined by discharge, transition to mechanical ventilation and/or if the patient is unable to continue i.e. death or feasibility impossible. The following will be recorded:

- Study Measurements:
 - Height/Wt, BMI, Temperature, Blood Pressure, O₂ Saturation, PaO₂/FiO₂ ratio, Shortness of Breath, Cough
- Labs (Standard of care)
 - Pro-Calcitonin, C-reactive protein, Ferritin, D-Dimer, CBC with differential,

Comprehensive metabolic panel

- Labs (Research) Early am blood draw (before 10 am)
 - TNF- α , IL-1 β , IL-6
- VNS stimulations
 - Total number of gammaCore® treatments administered, dates/times
- Daily Tx Log
 - Oxygen Required, Oxygen level (%) based on device type (HFNC / NC / Bipap / Optiflow), Ventilator Dependence (Yes / No), Date and time of Ventilation, Patient discharge home (Yes / No), Date and time (in 24 hour format) of Discharge, Survival (Yes / No) with Date and Time of Death
- Clinical Improvement Ordinal Scale
 - Concomitant medication and adverse events assessment

3 LIST OF ABBREVIATIONS AND DEFINITION OF TERMS

3.1 List of Abbreviations

ADE	Adverse Device Effect
AE	Adverse Event
ARDS	Acute Respiratory Distress Syndrome
CAP	Cholinergic Anti-inflammatory Pathway
CIP	Clinical Investigation Plan
CRF	Case Report Form
DMC	Data Monitoring Committee
FAS	Full analysis set
FEV1	Forced Expiratory Volume
IEC	Independent Ethics Committee
IL	Interleukin
nVNS	Non-Invasive Vagus Nerve Stimulation
PPS	Per protocol set
SADE	Serious Adverse Device Effect
SAE	Serious Adverse Event
SOB	Shortness of Breath
Soc	Standard of Care
IRB	Institutional Review Board
UAE	Unanticipated Adverse Event
UADE	Unanticipated Adverse Device Effect
USADE	Unanticipated Serious Adverse Device Effect
VNS	Vagus Nerve Stimulation
WOB	Work of Breathing

